# 5 Safety Reporting

# 5.1 Adverse Events (AEs)/ Serious Adverse Events (SAEs)

All AEs/SAEs occurring during the study observed by the investigator or reported by the participant, attributed to the study, will be recorded on the CRF. The relationship of AEs/SAEs to the study will be assessed by a medically qualified investigator.

AEs will be recorded on the AE Record Sheet and periodically discussed by the study steering group committee as required. Any safety concerns arising from the team will be reported to the Sponsor as soon as possible.

All SAE information must be recorded on an SAE form and sent to the Sponsor using the appropriate reporting form and the contact details on there within 24 hours of the study team being made aware of the SAE.

Any adverse event/serious adverse event occurring whilst a participant is continuing in the study, whether or not attributed to the study, will be documented in the study publication.

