### 1.2.2 Randomisation

Participants will be randomised 1:1; stratified by gender (male; female) and ethnicity (White European; other) to either intervention or control groups.

If two people are taking part from the same household they will be randomised to the same arm to prevent contamination taking place.

Both control and intervention participants will be informed of the outcome of the randomisation. In addition intervention participants will be sent a letter confirming the date and the venue of the education sessions.

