### **1.2.3 Study treatment interventions**

This will be a randomised control trial with an intervention group and a control group.

1) Intervention group: Those randomised to the intervention group will be invited to attend four patient-centred education sessions of the structured education programme and to receive regular reminders with Short Message Service (SMS) messages (text messages) after the first session. The programme focuses on promotion of personalised physical activity and health-related self-management activities, which impact on quality of life.

These structured education sessions have been developed during an iterative process in conjunction with PPI work and other stakeholders through the use of existing infrastructure consisting of Diabetes Education and Self-Management in on-going and Newly Diagnosed (DESMOND) groups and a network of trained facilitators.

2) Control group: No change in the usual care of these participants will take place and they will continue with their routine care management in line with their direct care team's current recommendations for people with multimorbidity.

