### **1.2.6** Sample size calculations

The primary outcome is change from baseline to 12 months average daily physical activity, as quantified by the Euclidean norm minus one (ENMO) method measured in milligravity units (mg). This is the main measure of activity derived from the activity monitor. In order to detect a minimum clinically significant difference of 2.1 mg, which is equivalent to an overall increase in physical activity volume of approximately 30 minutes of light walking at 4km/h, assuming a standard deviation of 5.3 mg [1], a power of 80% and significance level of 5%, the sample size requires 202 participants. To allow for 20% loss to follow-up and 20% non-compliance of the activity monitor, we will therefore need to recruit 338 participants (169 in each group).

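### SAP section 5.1 limits CRF recording to adverse events attributed to the study but promises to publish all of them, and does not say which record supplies the published events

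*SAP*

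**What the plan says.** Section 5.1 of the SAP contains five statements that bear on this point.

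- **CRF:** AEs and SAEs that are "attributed to the study, will be recorded on the CRF".
- **Attribution:** "The relationship of AEs/SAEs to the study will be assessed by a medically qualified investigator".
- **AE Record Sheet:** "AEs will be recorded on the AE Record Sheet and periodically discussed by the study steering group committee as required".
- **SAE form:** "All SAE information must be recorded on an SAE form and sent to the Sponsor", within 24 hours of the team becoming aware.
- **Publication:** any event during participation, "whether or not attributed to the study, will be documented in the study publication".

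Two statements elsewhere matter for comparing the arms. Section 1.2.2 says "Both control and intervention participants will be informed of the outcome of the randomisation". Section 1.2.3 says of the control group that "No change in the usual care of these participants will take place", while the intervention group is offered four education sessions and text messages promoting physical activity.

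**The concern.** The events to be published are a wider set than the events to be entered on the CRF. A CRF kept as written will lack every event judged unrelated to the study, yet the publication is to document those events. Someone completing forms, and later the trial statistician, cannot tell from section 5.1 which scope applies.

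There is a second, conditional issue. If an event must be attributed to the study before it is recorded, capture depends on a judgement that may be made differently in the two arms. An intervention participant who falls while walking more has a programme to which the fall can be ascribed; a control participant does not.

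Participants are aged 40 to 85 with two or more chronic conditions (section 1.2.4), so unrelated illness is to be expected in both arms, and half of them are encouraged to be more active. Event counts by arm can be interpreted only if both arms are captured under the same rule. The primary analysis is not touched; the safety report is.

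**Working it through.** The SAP has no figure to reproduce: it gives no event rate, no attribution share and no planned between-arm safety analysis. The check is therefore mainly a comparison of the text.

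**Step 1. Scope of each statement in section 5.1**

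| Record or output | Events covered | Attribution limit stated? |
|---|---|---|
| CRF | AEs and SAEs | Yes, attributed only |
| AE Record Sheet | AEs | No |
| SAE form | All SAE information | No |
| Publication | AEs and SAEs | Expressly none |

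The first and last rows conflict. The two middle rows could bridge the gap, but only if those records stand apart from the CRF and are used as the source for the publication. The section states neither.

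**Step 2. What follows for each type of event**

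- *SAEs, attributed or not:* the SAE form sentence covers them, so the data probably exist.
- *Non-serious AEs, attributed:* covered by the CRF sentence.
- *Non-serious AEs, not attributed:* covered only if the AE Record Sheet is not bound by the CRF limit. This is where the gap lies.

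**Step 3. Illustration of what a CRF limit would do**

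The only input from the SAP is 169 participants per group (section 1.2.6). The true risk and the attributed shares are assumptions chosen to show the mechanism. The calculation takes one event per affected participant and equal true risk in both arms.

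Events on the CRF per arm = 169 × true risk × attributed share.

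With a true risk of 40%, true events are 169 × 0.40 = 67.6 per arm.

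| Attributed share, intervention / control | On CRF, intervention | On CRF, control |
|---|---|---|
| 10% / 2% | 67.6 × 0.10 = 6.8 | 67.6 × 0.02 = 1.4 |
| 20% / 5% | 67.6 × 0.20 = 13.5 | 67.6 × 0.05 = 3.4 |
| 10% / 10% | 6.8 | 6.8 |

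For true risks of 20% to 60% (33.8 to 101.4 true events per arm) and unequal shares from 5% / 0% to 20% / 5%, the CRF would hold 1.7 to 20.3 intervention events and 0 to 5.1 control events.

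Two things follow. The imbalance between arms depends wholly on the attributed shares differing; with equal shares it disappears. The loss of unattributed events from the CRF does not depend on that: at a 10% share in both arms, 67.6 − 6.8 = 60.8 events per arm, or 90%, are absent from the CRF.

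**The case against.** The strongest reply is that section 5.1 does not in fact discard unattributed events. Only the CRF sentence carries the limit. The AE Record Sheet and SAE form sentences do not, and the latter speaks of all SAE information, which would include serious falls, injuries and cardiac events. The sentence on relationship assessment also implies that events are captured before attribution is decided. On this view the first sentence is loosely drafted. What goes on the CRF may be settled in the protocol, to which the SAP's introduction refers the reader for study conduct.

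Much of this stands. A reader might infer that only attributed events are recorded anywhere, so that the published account could not be produced. The documents do not support that, least of all for SAEs. Nor does the SAP promise a safety table or a between-arm test; it promises that events will be documented.

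A reader might also infer that control counts would be close to zero and that the safety record is biased against the intervention arm. The SAP gives no figure for this. The stated criterion is attribution to the study, not to the programme, and control participants also take part in study procedures such as accelerometer wear and clinical measurements (section 2.2). Participants know their allocation, but the SAP does not say whether the person judging attribution does.

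The objection does not remove the conflict between the CRF and publication sentences. Both rules are stated in this SAP, in its final version, and nothing in it says how the other two records resolve them.

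**Conclusion.** The point holds as an internal contradiction with a limited practical consequence. The CRF scope is narrower than the publication scope, and the SAP names no source record for the published events. Non-serious AEs not attributed to the study may be missed; SAEs are probably preserved on the SAE form.

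Arm-dependent capture is plausible if attribution stays the condition for recording, because only one arm receives a programme. It remains a reasoned possibility: its size cannot be obtained from the SAP, and the illustrative counts rest on assumed risks and shares. The conclusion about non-serious events assumes that the AE Record Sheet may inherit the CRF limit. If the trial can show that the Record Sheet is separate and unrestricted, and that it feeds the publication, what remains is a wording correction. The change is worth making because it is cheap and affects whether the safety report is complete.

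**What to change.** Reconcile the sentences in section 5.1 so that the recording scope matches the reporting promise:

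1. State that AEs and SAEs in both arms are recorded irrespective of attribution, with the attribution judgement held as a separate field.
2. Say whether the AE Record Sheet is part of the CRF, and name the record or records from which published events are drawn.
3. Say that events will be summarised by randomised arm, for example participants with at least one event and number of events, for AEs and SAEs separately.
4. Where unattributed events were not collected and cannot be recovered, restrict the publication sentence to what was recorded and report that limitation. SAP version 1.0 is dated September 2019 and protocol V6 June 2018, so collection may already have been under way and editing the SAP would not restore events never recorded.

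The cost is a wording change in the SAP and the CRF guidance, kept consistent with the protocol, and somewhat more AE recording at existing contacts. The primary analysis and sample size are unaffected.
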